5. STUDY DESIGN

Participants will be pre-randomised based on the hospital sites they are attending. Northumbria Specialist Emergency Care Hospital (NSECH) and James Cook University Hospital (JCUH) are the two nominated research sites. Initially the two participating sites will be randomised to either intervention or control site. After six months duration the sites will reverse and whichever site was originally randomised as intervention site will become the control site for the remaining six months and the control site will become the intervention site.

The participants will be selected by the attending trained North East Ambulance Service (NEAS) personnel and enrolled into the study if they are positive for a mechanism of injury and clinical assessment that would suggest a Spinal Cord Injury. NEAS are acting as the Participant Identification Centre (PIC) for patient participants and research site for clinical experience.

Control group: Over a six-month period this group will be managed in the traditional manner. This will involve patients being advised of the need for a hard collar, blocks and tape. For a variety of reasons this may not be tolerated by some patients and this non-compliance will be recorded for the purposes of the study outcome results, although these patients will be included in the 'traditional' method of motion restriction numbers.

Intervention group: Over a six-month period intervention group patients transported by NEAS crews with a suspected cervical spine injury being taken to the randomised intervention site with their cervical spine motion restriction managed in accordance with the proposed flow chart (appendix B). For these patients unless the exclusion criteria apply, no hard collars will be employed.

After the initial six-month intervention/control phase the receiving sites will reverse the process and undertake another six month phase as the control/intervention phase.

Each participant enrolled will be followed up on site by a research clinician and clinical outcomes measured as stated on the Computerised Tomography (CT) report and/or patient notes. Patient experience outcomes will be collected by a research clinician using a dementia friendly adapted Likert scale type survey prior to discharge or at 72 hours whichever is earliest. Participants will also be

CONFIDENTIAL: Spinal Motion Restriction Feasibility Study (SMRFS).

consented at this point. It is expected that only one visit will be required unless participants wish to delay consent to consider the information.

Participant outcome measures will include:

- Time: on scene, to scan, in Emergency Department.
- Neurology (Gross)
- Fractures/Injury
- Tissue Viability/Pressure sores
- Compliance

Participant experience outcome measures will include:

- Comfort
- Pain
- Understanding
- Complications (anxiety, breathing)

Additional data will be obtained from a clinicians experience of managing SCI patients within the SMRF Study. A simple clinician experience questionnaire will be completed after each participant has been managed by a SMRF Study clinician.

Data will be collected in a Microsoft excel spread sheet and analysis will be undertaken using Statistical Package for the Social Sciences (SPSS) version 22.0.

Free text from the patient and clinician experience questionnaire will be coded and analysed using NVivo qualitative data analysis Software; QSR International Pty Ltd. Version 11, 2015.

6. PARTICIPANT IDENTIFICATION

6.1. Study Participants

NEAS will act as the Participant Identification Centre (PIC). Participants will include those patients who have experienced a mechanism of injury that would suggest a potential SCI. No upper age exclusions or pregnancy restrictions will apply. Those aged less than 18 will be excluded.

6.2. Inclusion Criteria

Inclusion Criteria

Any participant aged 18 years and older may enter the study if ANY of the following apply:

- Participant has had a mechanism of injury suggestive of SCI. Example mechanisms include (but not exclusive too) RTC's, falls from height, serious assaults AND transported by NEAS crew to either NSECH or JCUH. In the elderly or frail patient this may include a fall from standing height and should be based on a thorough clinical exam (see appendix A),
- Symptoms consistent with cervical spine injury (note for older patients any neck pain including muscular should be considered as suspicious for cervical spine injury),
- Those with dementia/delirium who are unable to communicate reliably regarding potential injury consider those with significant head injury as at risk of potential cervical spine injury and include them in study.

6.3. Exclusion Criteria

Exclusion Criteria

The participant may **NOT** enter the study if ANY of the following apply:

- Children aged <18 years,
- Those patients NOT transported to NSECH or JCUH,
- Participant requires airway support for whatever reason,
- The participant has a GCS ≤13,
- The participant is displaying obvious signs of new neurology such as paralysis,
- The participant has significant facial injuries that may benefit from the support a rigid collar may provide.
- The participant has already been immobilised with a rigid collar by a non-study clinician or third party provider prior to **intervention group** clinician assessment.

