7.2. Screening and Eligibility Assessment

The participants will be screened for eligibility by the attending crew based on the Spinal Motion Restriction Screening Tool in appendix A and inclusion/exclusion criteria applied. These clinicians are employed by North East Ambulance Service who are acting as the Participant Identification Centre (PIC)

for patient participants and will also act as a research site for the clinician experience element of the study.

If the patient is positive for immobilisation using the screening tool (appendix A) and in the catchment area of the nominated receiving research sites which will be Northumbria Specialist Emergency Care Hospital (NSECH) at Cramlington, Northumberland or James Cook University Hospital (JCUH) at Middlesbrough then they will be identified as a potential participant in the SMRFS intervention or control group.

Age (unless aged less than 18 years), sex, previous medical history or pregnancy status will not be used to exclude participants.

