The participant or parent/guardian or legally authorised representative must personally sign and date the latest approved version of the Informed Consent form before any information will be included in the study. CONFIDENTIAL: Spinal Motion Restriction Feasibility Study (SMRFS).

Written and verbal versions of the Participant Information Sheet and Informed Consent will be presented to the participants or participants carers detailing no less than: the exact nature of the study; what it will involve for the participant; the implications and constraints of the study; the known side effects and any risks involved in taking part. It will be clearly stated that the participant is free to withdraw from the study at any time for any reason without prejudice to future care, without affecting their legal rights, and with no obligation to give the reason for withdrawal.

Capacity shall be assessed on the basis of the patient being able to understand the nature and purpose of the project, the risks and benefits of taking part and can demonstrate that they have retained and weighed up the information before making an informed choice.

Those with dementia and/or delirium will be included in this part of the study and if they are unable to consent themselves consent will be sort from the next of kin or person with power of attorney.

The participant/carer will be allowed as much time as wished to consider the information, and the opportunity to question the Investigator, their GP or other independent parties to decide whether they will participate in the study. Written Informed Consent will then be obtained by means of participant dated signature and dated signature of the person who presented and obtained the Informed Consent. The person who obtains the consent will be suitably qualified, experienced and have been authorised to do so by the Chief/Principal Investigators. A copy of the signed Informed Consent will be given to the participant. The original signed form will be retained at the study site and scanned to a secure folder held on the North East Ambulance Service network.

Clinicians who are involved within the study and completing a clinician experience questionnaire will also be consented using the above principles after undertaking training.

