7.7. Discontinuation/Withdrawal of Participants from Study

Each participant has the right to withdraw from the study at any time. In addition, the Investigator may discontinue a participant from the study at any time if the Investigator considers it necessary for any reason including:

- Pregnancy
- Ineligibility (either arising during the study or retrospectively having been overlooked at screening)
- Significant protocol deviation
- Significant non-compliance with treatment regimen or study requirements
- Withdrawal of Consent
- Loss to follow up

After the initial participant visit for the participant experience questionnaire and collection of data from participant notes no further observations will be required.

Withdrawal of consent from a participant will exclude the data for that participant from analysis.

Withdrawn participants will NOT be replaced.

The reason for withdrawal will be recorded in the CRF.

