8. INTERVENTIONS

The flow chart for all participants in the Spinal Motion Restriction Feasibility Study is shown in appendix D.

Intervention group: Over a six-month period intervention group patients (suspected cervical spine injury – see appendix A for guidelines) will be transported by NEAS crews to the randomised intervention site. See appendix B for SMRF Study Intervention Group Guideline.

Participants will have their cervical spine motion restriction managed in accordance with the proposed flow chart (see appendix B). For these patients unless the exclusion criteria apply, NO rigid collars will be used. The control group will follow existing clinical guidelines and use a rigid collar (appendix E).

9. SAFETY REPORTING (Adverse Event Management)

Use of hard collars in association with blocks and tapes in the manner described above has been accepted practice to reduce the risk of further damage due to movement of potentially unstable injuries for many years. Although there appears to be mounting expert opinion that the application of hard collars may cause more harm than good we must be vigilant against the potential of causing more harm in these patients. If there should be a case of new neurology developing post transfer during the study period the trial would need to be halted while a full and thorough investigation was undergone into whether the use of or lack of a hard collar caused or contributed to deterioration in neurological function. This study is not aimed at underplaying the risk of SCI or the need for appropriate management.

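### The new-neurology exclusion has no time point and Section 7.7 allows ineligibility to arise after entry, so a patient who worsens during transport may be ruled out on the finding that is itself an outcome

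*Protocol*

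**What the plan says.** **Entry.** Section 6.3 lists conditions under which a patient may not enter. Three describe a clinical state: "The participant is displaying obvious signs of new neurology such as paralysis", "The participant has a GCS ≤13" and "Participant requires airway support for whatever reason". None is dated. The only criterion tied to a clinical assessment is the prior rigid collar, which must have been applied "prior to intervention group clinician assessment". Section 7.2 says who applies the list: "The participants will be screened for eligibility by the attending crew". Sections 5 and 8 say that the intervention group has no rigid collar unless an exclusion applies.

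**After entry.** Section 7.7 lets the investigator discontinue a participant at any time, and one of the listed grounds is "Ineligibility (either arising during the study or retrospectively having been overlooked at screening".

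**Outcome and safety.** Section 5 lists gross neurology as a participant outcome. The opening of Section 9 says: "If there should be a case of new neurology developing post transfer during the study period the trial would need to be halted". Section 9.2 separately calls for a report and a halt on an obvious change from before to after management in the intervention group compared with control.

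**Data.** Under Section 7.3 the participant or representative "must personally sign and date the latest approved version of the Informed Consent form before any information will be included in the study". Section 7.6 has the notes reviewed once consent is obtained. Patients are approached in the emergency department after the CT report, or up to 72 hours if admitted. Section 7.5.4 states that the hospital research clinicians are not blinded.

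**The concern.** One finding, new gross neurology, is an exclusion, an outcome and a safety trigger. That is workable only if the protocol says when it stops being the first and becomes the others. The sequence can be inferred, but no sentence in the protocol text says that eligibility is closed once the crew has assessed the patient, and Section 7.7 says it can reopen.

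Take a patient with no deficit at scene, managed as allocated, who has new gross neurology on arrival. Staff who know the allocation and the neurological result could apply Section 6.3 as written, or use the Section 7.7 ground, and treat the patient as ineligible. Removal would then depend on the outcome. It could happen in either arm and would push the neurology comparison towards no events. In a study that omits the collar in one arm, this is the clinical finding that matters most for safety.

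**Working it through.** The protocol has no power calculation (Section 10.3) and no deterioration rate, so there is no stated figure to reproduce. The check is a comparison of texts, followed by a short illustration of scale.

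**Step 1. Is there a time point?** Section 6.3 gives none for neurology, GCS or airway support. Sections 5, 7.2 and 8 imply one: the crew screens, and the exclusions govern whether a collar is used, so they must be judged before that decision. The time point is implied, not stated as final.

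**Step 2. Can eligibility change afterwards?** Section 7.7 says yes. Of the Section 6.3 criteria, age and a collar already in place cannot newly arise once management has begun, and destination is settled on arrival. Neurology, GCS and airway need can change. The clause therefore bears chiefly on changes in the patient's condition.

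**Step 3. Which of these are also outcomes?**

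| Finding | Dated exclusion? | Named outcome? | Named halt trigger? |
|---|---|---|---|
| New gross neurology | No | Yes (Section 5) | Yes (Section 9) |
| GCS 13 or below | No | No | No |
| Airway support | No | No; breathing complications are an experience item | No |

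The direct overlap is shown for neurology only.

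**Step 4. Would the case be lost?** There are two routes.
- *Ruled ineligible before consent.* Sections 7.3 and 7.6 keep the patient's information out of the study until consent is signed. Intention to treat does not recover the case, because sites rather than patients are randomised (Section 7.4) and the patient never becomes a counted participant.
- *Discontinued after consent.* Section 7.7 states exclusion of data only for withdrawn consent, so data already collected should stay.

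The first route is the weaker point of the protocol.

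**Step 5. Do the safety rules cover transport?** Section 9 speaks of neurology developing after transfer. Section 9.2 speaks of change across management. Onset during transport falls within the second and is unclear under the first.

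**Step 6. Scale (illustration only).** Inputs are N = 100 patients (50 per arm, synopsis) and an assumed event rate p. Section 3 cites less than 0.5% confirmed spinal cord injury among potential cases. That is a different event, so 0.5% serves only as a middle value in a range.

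P(at least one event) = 1 − (1 − p)^100

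- p = 0.1%: 1 − 0.999^100 = 9.5%
- p = 0.5%: 1 − 0.995^100 = 39.4%; expected events 100 × 0.005 = 0.5
- p = 1%: 1 − 0.99^100 = 63.4%

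If one event occurs in an arm of 50 and that patient is removed, the observed proportion goes from 1/50 = 2% (exact 95% CI 0.05% to 10.6%) to 0/49 = 0% (exact 95% CI 0% to 7.3%).

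**The case against.** The strongest reply is that the sequence is clear enough. Section 5 has crews select and enrol patients on mechanism and clinical assessment, Section 7.3 says enrolment happens during the traumatic event, and consent is retrospective and covers use of information only. The present-tense exclusions in a list governing entry read naturally as status at crew screening. The Appendix A screening tool and the Appendix D flow chart are not reproduced in the copy reviewed and may show the order of steps. This stands. A reader might infer from the late consent that formal entry follows treatment, or that nothing places the exclusions in time, and the text does not support either.

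A reader might also infer that the protocol directs removal of patients who deteriorate. It does not. The Section 7.7 power is discretionary, the primary analysis is by intention to treat (Section 10.1), data exclusion is stated only for withdrawn consent, and Section 9.2 would call for reporting of a change across management. Section 7.6 also records any neurology and its time after injury, and Sections 7.5.1 and 13.2 audit ambulance data for missed eligible patients.

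Two further readings go too far. GCS and airway support cannot be treated as outcomes that double as exclusions: neither is a named outcome, and the GCS criterion is a threshold, not a fall. Nor is 39% the chance of deterioration in this study, because the underlying 0.5% concerns confirmed injury.

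What the reply leaves unanswered is Section 7.7. It is a stated rule that ineligibility can arise after entry, and nothing in the text says that new neurology is outside it.

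**Conclusion.** The concern holds for new neurology. The protocol permits, without prescribing, removal of a participant on a finding that is also an outcome and a halt trigger, at the discretion of unblinded staff. The exposure is greatest for a patient ruled ineligible before consent, whose notes would not be reviewed. GCS and airway support share the missing time point but not the overlap with a named outcome.

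The size cannot be computed from the document. At assumed rates of 0.1% to 1%, the chance of at least one event among 100 patients is about 10% to 63%, so there may well be none. If there is one, losing it could leave an arm with no observed events. This assumes independent patients, a common rate and full recruitment. In a feasibility study declared underpowered, this is a fault of wording to correct, not evidence that the results will be biased.

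**What to change.** - **Sections 6.3 and 7.2:** state that eligibility is fixed at the crew's assessment before spinal motion restriction is applied and is not reassessed on later findings. One sentence would cover neurology, GCS and airway support together.
- **Section 7.7:** delete the words that let ineligibility develop after entry. Limit the ground to facts already present at that assessment and found later to have been overlooked.
- **Sections 5 and 10:** state that new neurology appearing after that assessment stays in the allocated arm as an outcome and is reported under Section 9.
- **Sections 9 and 9.2:** reconcile the two descriptions of the period covered, so that the position of onset during transport is explicit.

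The cost is a protocol wording amendment. No extra visit or data item is needed, since Section 7.6 already records neurology with its time after injury.

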7. STUDY PROCEDURES

7.1. Recruitment

Potential participants will be identified by the trained recruiting ambulance personnel based upon the mechanism of injury and a clinical examination suggestive of a SCI as per the Spinal Motion Restriction Screening Tool in appendix A. Clinicians will be NEAS employees and NEAS are acting as the Participant Identification Centre (PIC) throughout the study. Clinicians who volunteer for the study will have also consented to undertake a Clinician Experience Questionnaire after each participant interaction.

7.2. Screening and Eligibility Assessment

The participants will be screened for eligibility by the attending crew based on the Spinal Motion Restriction Screening Tool in appendix A and inclusion/exclusion criteria applied. These clinicians are employed by North East Ambulance Service who are acting as the Participant Identification Centre (PIC)

for patient participants and will also act as a research site for the clinician experience element of the study.

If the patient is positive for immobilisation using the screening tool (appendix A) and in the catchment area of the nominated receiving research sites which will be Northumbria Specialist Emergency Care Hospital (NSECH) at Cramlington, Northumberland or James Cook University Hospital (JCUH) at Middlesbrough then they will be identified as a potential participant in the SMRFS intervention or control group.

Age (unless aged less than 18 years), sex, previous medical history or pregnancy status will not be used to exclude participants.

7.3. Informed Consent

There will be information communicated to the public prior to the initial roll out asking patients to opt out if they wish in advance. Following this initial inclusion in the study will be assumed. A website has been made available to the public during this study:

https://www.neas.nhs.uk/our-services/research-and-development/smrf.aspx

The study relates directly to patients who have experienced an acute traumatic event which is unpredictable and delaying management may be detrimental and, therefore, consent to access patient records will be delayed until the sub-acute phase of care in the Emergency Department. Consulting a carer or registered medical practitioner without placing the participant at risk of harm from delaying emergency treatment is not appropriate.

Eligible participants (see section 7.2) will be given the 'Participant Information Sheet' (see appendix C) by the trained transporting crew on arrival at either study receiving site (NSECH/JCUH).

As participants will be enrolled into the study during a traumatic event, they will be in a compromised, pained state and need immediate care. To ask for consent at that juncture would delay care and surmount to no more than a signature with little comprehension by the participant. If minimal risk is presented to the participant (substituting one form of spinal motion restriction for another), then respecting patient' rights and dignity accompanies being able to understand what they are being asked.

Participants' care will proceed almost exactly as it would have with or without the study, the patients are not uniquely imposed with non-clinical risks or burdens, and will be given the best quality care available to them based on current evidence. It is unknown (before the study) whether traditional immobilisation or new spinal motion restriction (no hard collar) presents a better treatment, and therefore participants would have been treated with one through an arbitrary decision.

Consequently, this study is not looking to consent the participant into undertaking an intervention but will retrospectively consent the patient after the event to allow the research team to use their information within the study.

The participant or parent/guardian or legally authorised representative must personally sign and date the latest approved version of the Informed Consent form before any information will be included in the study. CONFIDENTIAL: Spinal Motion Restriction Feasibility Study (SMRFS).

Written and verbal versions of the Participant Information Sheet and Informed Consent will be presented to the participants or participants carers detailing no less than: the exact nature of the study; what it will involve for the participant; the implications and constraints of the study; the known side effects and any risks involved in taking part. It will be clearly stated that the participant is free to withdraw from the study at any time for any reason without prejudice to future care, without affecting their legal rights, and with no obligation to give the reason for withdrawal.

Capacity shall be assessed on the basis of the patient being able to understand the nature and purpose of the project, the risks and benefits of taking part and can demonstrate that they have retained and weighed up the information before making an informed choice.

Those with dementia and/or delirium will be included in this part of the study and if they are unable to consent themselves consent will be sort from the next of kin or person with power of attorney.

The participant/carer will be allowed as much time as wished to consider the information, and the opportunity to question the Investigator, their GP or other independent parties to decide whether they will participate in the study. Written Informed Consent will then be obtained by means of participant dated signature and dated signature of the person who presented and obtained the Informed Consent. The person who obtains the consent will be suitably qualified, experienced and have been authorised to do so by the Chief/Principal Investigators. A copy of the signed Informed Consent will be given to the participant. The original signed form will be retained at the study site and scanned to a secure folder held on the North East Ambulance Service network.

Clinicians who are involved within the study and completing a clinician experience questionnaire will also be consented using the above principles after undertaking training.

